Copies of the CRF will be kept on site. The original CRF pages must be sent to the HOVON Data Center at the requested timepoints. How and when to send in forms is described in detail in the CRF

header and the CRF instructions.

All data from the CRF will be entered into the study database by the HOVON Data Center.

16 Randomization

Eligible patients should be registered within 2 months of diagnosis. Patients can be registered at the HOVON Data Center of the Erasmus MC – Daniel den Hoed by phone call: [name] or [contact] Monday through Friday, from 09:00 to 17:00, or via the Internet through TOP (Trial Online Process; <https://www.hdc.hovon.nl/top>). A logon to TOP can be requested at the HOVON Data Center for participants.

The following information will be requested at registration:

- ◆ Protocol number
- ◆ Institution name
- ◆ Name of caller/responsible investigator
- ◆ Patient's initials or code
- ◆ Patient's hospital record number (optional)
- ◆ Sex
- ◆ Date of birth
- ◆ Date of diagnosis CML
- ◆ Eligibility criteria

All eligibility criteria will be checked with a checklist. Patients will be randomized, stratified by center and Sokal score with a minimization procedure, ensuring balance within each stratum and overall balance. The randomization result and a unique patient study number will be given immediately by TOP or phone and confirmed by fax or email.

17 Statistical considerations

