Data from the IRIS-study show the impact of MMR, as they did not observe any progression of death in patients who were in MMR at 12 months, for a follow up period of 12-18 months. However, because long-term follow up data of patients who achieve a MMR are lacking, we will consider MMR at 12 months as the primary end point for this trial.

Patients who have achieved a MMR at 12 months after randomization, will be considered a success. Patients will be considered a failure in case of:

- ◆ loss of hematological, cytogenetic or molecular response, accelerated phase, blastic crisis, clonal evolution or death before 12 months;
- ◆ no MMR achieved within 12 months.

In order to detect with 80% power an improvement in 12-months' MMR from 60% to 75% (2-sided significance level $\alpha=0.05$), 330 patients are required. This will be achieved in about 5 years, as an accrual of 60-70 patients per year is expected.

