17.2.1 Efficacy analysis

The main endpoint for the comparison between the two treatment arms is the proportion of patients

with a MMR at 12 months. The proportions will be compared between the two treatment arms using logistic regression. In addition, an exploratory logistic regression with adjustment for baseline Sokal score will be performed to evaluate the effect of Sokal score on the MMR rate at 12 months.

Secondary end points include the rates of hematological response, complete cytogenetic response (CcyR), major molecular response (MMR) and complete molecular response (CMR), time to CcyR, MMR and CMR, progression-free survival and overall survival from randomization.

Actuarial survival curves for all time-to-event end points will be computed using the Kaplan-Meier method, 95% confidence intervals will be constructed, and survival curves will be compared using the log-rank test for illustrative purposes, without and with stratification based on the Sokal score.

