17.4 Interim analyses and safety monitoring

One formal interim analysis is focused on efficacy and is planned, primarily to guard against unfavorable results in the experimental arm (imatinib + cytarabine). This analysis will be performed after 12-months molecular response data of the first 150 patients (75 per treatment arm) are available, and is expected to take place 3.5-4 years after the start of the trial.

The DSMB is free in its recommendations to the study coordinators, but the following guidelines apply:

- ♦ A worse 12-months' MMR-rate in the experimental arm with a P-value < 0.1 is a good reason to recommend the stopping of the trial or recommendations for modifications.
- ♦ A better 12-months MMR-rate in the experimental arm is in general no reason to recommend early stopping of the study, unless the associated P-value is very extreme ($P < 0.001$).

The study will be closely and sequentially monitored before the interim analysis. Monitoring will be based on the reported SAE's which are not subjected to data delay. The difference in the number of patients with an SAE in both arms and the difference in the number of deaths in both arms are tested using the binomial test. It will be repeatedly tested whether those incidences in the experimental arm are higher at a significance level of 0.05, adjusted for multiple testing (adjustment based on simulation). If one of both incidences is significantly higher in the experimental arm an early report will be presented to the DSMB.

18 Ethics

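### The randomisation is balanced on Sokal score but the primary MMR model omits it, so the primary test is conservative to the extent that Sokal predicts response

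*Protocol*

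**What the plan says.** Protocol section 16 states that "Patients will be randomized, stratified by center and Sokal score with a minimization procedure". Section 11 confirms that the Sokal score is determined centrally and used for stratification before randomisation.

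In section 17.2.1 the main endpoint is the proportion of patients with MMR at 12 months, compared between arms by logistic regression with no covariate named. The same paragraph adds "an exploratory logistic regression with adjustment for baseline Sokal score will be performed", and gives its purpose as evaluating what Sokal does to the MMR rate. The log-rank tests for time-to-event endpoints are planned without and with Sokal stratification and are described as illustrative.

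Section 17.1 sizes the trial on "an improvement in 12-months' MMR from 60% to 75"%, at 80% power and two-sided 0.05, and concludes that "330 patients are required". Section 17.2.3 names the Sokal score first among the prognostic factors to be studied for 12-month MMR. Section 17.4 plans one interim MMR comparison on 150 patients, mainly to detect harm in the cytarabine arm, with P < 0.1 as the guideline for a worse result. It names no model.

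**The concern.** Forcing balance on a prognostic factor removes that factor's variation from the difference between the arms. A model that leaves the factor out still counts the variation as noise, so its standard error overstates how much the estimate really varies from trial to trial. The test then rejects a true null hypothesis less often than 5%, and it finds a real effect less often than a test that uses the factor.

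At stake is some efficiency in the primary comparison. The interim look is affected too: there, a conservative test is slower to flag an inferior experimental arm. The protocol itself gives the adjusted model its lower status, so this is a stated choice and not a detail left to a later analysis plan.

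**Working it through.** **1. The plan's own figure.** Inputs from section 17.1: 60% versus 75%, two-sided 0.05, 80% power. The 75 per arm in section 17.4 implies 1:1 allocation. With mean rate 0.675,

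n = [1.960 × √(2 × 0.675 × 0.325) + 0.842 × √(0.24 + 0.1875)]² / 0.15² = 151.9 per arm.

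With the continuity correction,

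n' = (151.9/4) × [1 + √(1 + 4/(151.9 × 0.15))]² = 164.9, so 165 per arm and 330 in total.

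The stated 330 is reproduced exactly, from an unadjusted comparison of two proportions. Without the correction, 165 per arm gives 83.2% power, so there is already a small reserve over 80%.

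**2. Inputs that the protocol does not give.** No MMR rates by Sokal group and no Sokal mix are reported. Assumed here: low/intermediate/high risk in 40/35/25% of patients, and four sets of control rates with an overall rate of 60%, running from no Sokal effect to a strong one.

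**3. Approximate size under the null.** The unadjusted model uses the variance p(1 − p) = 0.60 × 0.40 = 0.24 per patient. With arms balanced within Sokal groups, the variance that remains is 0.24 − B, where B = Σ w(p_group − 0.60)². The model standard error is too large by the factor r = √[0.24/(0.24 − B)], and the real type I error is 2Φ(−1.960 r). For 75/58/38%:

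- B = 0.40 × 0.0225 + 0.35 × 0.0004 + 0.25 × 0.0484 = 0.0212
- r = √(0.24/0.2188) = 1.047
- type I error = 2Φ(−2.053) = 4.0%

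The same steps give 4.7% for 68/59/49% (B = 0.0056, r = 1.012) and 3.0% for 82/57/29% (B = 0.0437, r = 1.106).

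**4. Simulation.** 330 patients, 20,000 trials per scenario, permuted blocks of 4 within Sokal group standing in for minimisation, logistic regression without and with Sokal group. Coverage is that of the unadjusted 95% interval under the null. Power is for marginal rates of 60% versus 75%. Gains are taken before rounding.

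| Control MMR, low/int./high | Type I error, unadjusted | Coverage | Power, unadjusted | Power, adjusted | Gain (points) |
|---|---|---|---|---|---|
| 60/60/60% | 5.1% | 94.9% | 83.2% | 83.4% | 0.2 |
| 68/59/49% | 4.6% | 95.4% | 83.5% | 84.1% | 0.6 |
| 75/58/38% | 4.0% | 96.0% | 84.8% | 86.7% | 2.0 |
| 82/57/29% | 3.2% | 96.8% | 85.4% | 89.3% | 4.0 |

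Adjusted type I error is 4.9 to 5.2% throughout. A separate simulation of 100,000 trials gave unadjusted type I errors of 5.0, 4.8, 4.1 and 3.0%, and power gains of about 0, 0.4, 1.8 and 3.6 points.

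**5. Where the gain comes from.** Adjustment does not shrink the printed standard error. In the strongest scenario the unadjusted log odds ratio averages 0.697 with standard error 0.241, a ratio of 2.89. The adjusted one averages 0.847 with 0.269, a ratio of 3.15. The estimate moves further from zero because the adjusted odds ratio is conditional on Sokal.

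**6. Interim harm check.** Assumptions: 150 patients, true MMR 60% in control and 45% in the experimental arm, a two-sided P < 0.1 in the unfavourable direction, and the same unadjusted model as in section 17.2.1. The chance of meeting the guideline is 57.2% unadjusted versus 61.9% adjusted for 75/58/38%, and 57.5% versus 64.9% for 82/57/29%. Across the four scenarios the gain is about 0, 2, 5 and 8 points.

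**The case against.** An unadjusted primary test is legitimate and errs only on the safe side for false positives. It matches the marginal proportions on which the trial was sized, and it reaches the planned power under every scenario examined. The adjusted model is already prespecified, so an adjusted estimate would be available in any case. All of this stands. What remains is which of two planned models carries the primary test.

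Four stronger readings are tempting and are not supported:

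- A reader might infer that the real type I error is below 5%. That holds only if Sokal predicts MMR, and the protocol gives no effect size; section 17.2.3 lists it as something still to be analysed.
- A reader might infer that adjustment would narrow the reported interval. It would not (step 5). The unadjusted interval is too wide only in the sense that it over-covers.
- A reader might see the primary analysis as out of line with the log-rank tests. Section 17.2.1 plans both an unadjusted and a Sokal version for each, and the log-rank tests are illustrative.
- A reader might take the three risk groups of Appendix B to be the minimisation categories. Sections 11 and 16 say only Sokal score.

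Center is also a minimisation factor and is also left out of the model. The same logic applies to it, but its effect was not quantified here, and a model with many centers is less practical than one with a single Sokal term.

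**Conclusion.** The point holds as a matter of efficiency, not validity. The design balances on Sokal and the primary model ignores it. Under an assumed 40/35/25% mix, type I error runs from about 5.0% with no Sokal effect to about 3.0% with a strong one, and 0 to 4 points of power are lost at the final analysis. The loss at the interim harm check may reach about 8 points if Sokal is strongly prognostic and the interim comparison is also unadjusted. If Sokal does not predict MMR, adjusting costs practically nothing. The direction is certain wherever Sokal is prognostic; the size depends on inputs that the protocol does not contain. The trial is not underpowered by its own standard: unadjusted power was 83 to 85% in the main simulation, against a planned 80%.

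**What to change.** In section 17.2.1, name as the primary test the treatment effect from the logistic regression that includes Sokal, in the form used for the minimisation (for example the Appendix B risk groups, if those were used), and state which form that is. Keep the unadjusted model as a sensitivity analysis. Because the adjusted odds ratio is conditional and its standard error will not be smaller, also report the MMR proportion in each arm and their difference, which is the scale on which the trial was sized. In section 17.4, state that the interim MMR comparison uses the same model.

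The cost is a few sentences. The Sokal score is determined before randomisation, the adjusted model is already planned, and 330 patients remain sufficient. Settling this before the comparative data are seen also removes any later choice between two models when the result lies close to P = 0.05.

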17.2.2 Toxicity analysis

The analysis of treatment toxicity will be done primarily by tabulation of the incidence of side effects and infections with CTCAE grade 2 or more (see appendix D) by treatment arm (and cycle cytarabine, arm B only).

17.2.3 Additional analyses

Additional analyses involve the analysis of prognostic factors, especially the Sokal score and Euro-hazard score (see appendix B), with respect to 12-months' MMR-rate, and time to MMR, PFS and OS. Logistic regression and Cox regression analysis will be used for this purpose.

17.3 Data and safety monitoring board

A data and safety monitoring board (DSMB) will be installed before start of the study. Results of the planned interim analysis stated in paragraph 17.4 and eventually other unplanned interim analyses, will be presented confidentially to the DSMB. Only if the DSMB recommends that the study should be stopped or modified, the results will become available to the principal investigator for further decisions. The presented reports include by treatment arm the number of entered patients and at that time evaluable patients, treatment given, the number of failures, types of failures and incidence of SAE's and other adverse events (CTCAE grade).

17.4 Interim analyses and safety monitoring

One formal interim analysis is focused on efficacy and is planned, primarily to guard against unfavorable results in the experimental arm (imatinib + cytarabine). This analysis will be performed after 12-months molecular response data of the first 150 patients (75 per treatment arm) are available, and is expected to take place 3.5-4 years after the start of the trial.

The DSMB is free in its recommendations to the study coordinators, but the following guidelines apply:

- ♦ A worse 12-months' MMR-rate in the experimental arm with a P-value < 0.1 is a good reason to recommend the stopping of the trial or recommendations for modifications.
- ♦ A better 12-months MMR-rate in the experimental arm is in general no reason to recommend early stopping of the study, unless the associated P-value is very extreme ($P < 0.001$).

The study will be closely and sequentially monitored before the interim analysis. Monitoring will be based on the reported SAE's which are not subjected to data delay. The difference in the number of patients with an SAE in both arms and the difference in the number of deaths in both arms are tested using the binomial test. It will be repeatedly tested whether those incidences in the experimental arm are higher at a significance level of 0.05, adjusted for multiple testing (adjustment based on simulation). If one of both incidences is significantly higher in the experimental arm an early report will be presented to the DSMB.

18 Ethics

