9.2 Imatinib and cytarabine combination therapy (arm B)

Following registration and randomization, preceding therapy with hydroxyurea or imatinib is stopped and imatinib is started at a total dose of 800 mg daily, preferably 2 x 400 mg. The first cycle of i.v. cytarabine is started as soon as possible, preferably within 14 days from the start of imatinib, and at the latest 4 weeks from the start of imatinib. Dose adaptations are outlined in section 9.2.1. During combination therapy, patients will receive imatinib at a total dose of 800 mg, preferably 400 mg twice daily, continuously. Cytarabine is added as a 7 day course of i.v. chemotherapy. Cytarabine is given at a dose of $200 \text{ mg/m}^2/\text{day}$ in 500 ml NaCl 0.65% (or 0.9%) as 1-2 hours infusion, once daily. The second cycle of cytarabine will be started if there is evidence of hematopoietic recovery (platelets $> 100 \times 10^9/l$ and WBC $> 2.0 \times 10^9/l$), when evaluation procedures after cycle I have been performed and when all toxicities have resolved to grade ≤ 1 . Cycle II should be started within 8 weeks from the start of cycle I. If start of cycle II within 8 weeks from start of cycle I is not possible, patients should continue with imatinib monotherapy.

Combination therapy may be administered on an outpatient basis. However, it is advocated to admit patients clinically in case of grade 4 hematological toxicity (e.g. ANC < $0.5 \times 10^9/l$). Alternatively patients may be followed up frequently (3 times per week) in the outpatient clinic, with immediate clinical admittance in case of fever.

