11.3 Evaluation of response

Response will be evaluated according to the criteria in appendix C. Response will be assessed after cycle I (arm B), after cycle II (arm B), after 3 months (arm A) and thereafter approximately every 6

months during imatinib monotherapy and follow up starting at 6 months after entry.

12 Toxicities

All chemotherapeutic agents used in the protocol can cause pancytopenia and can induce septic or hemorrhagic complications.

Cytarabine can cause anorexia, nausea, vomiting, hepatic dysfunction, skin rash, pneumonitis, fever.

Imatinib can cause nausea, muscle spasms, arthralgia, headache, peri-orbital edema and liverfunction abnormalities.

Toxicities will be scored according to the NCI Common Terminology Criteria for Adverse Events, version 3.0 (see appendix D).

13 Reporting serious adverse events

Adverse event (AE)

An adverse event (AE) is any untoward medical occurrence in a patient or clinical study subject during protocol treatment. An AE does not necessarily have a causal relationship with the treatment. An AE can therefore be any unfavorable and unintended sign (including an abnormal laboratory finding), symptom, or disease temporally associated with the use of a medicinal (investigational) product, whether or not related to the medicinal (investigational) product.

Adverse reaction (AR)

Adverse reactions (AR) are those AE's of which a reasonable causal relationship to any dose administered of the investigational medicinal product and the event is suspected.

Serious adverse event (SAE)

A serious adverse event is defined as any untoward medical occurrence that at any dose results in:

- death
- a life-threatening event (i.e. the patient was at immediate risk of death at the time the reaction was observed)
- hospitalization or prolongation of hospitalization
- significant / persistent disability
- a congenital anomaly / birth defect
- any other medically important condition (i.e. important adverse reactions that are not immediately life threatening or do not result in death or hospitalization but may jeopardize the patient or may require intervention to prevent one of the other outcomes listed above)

Note that ANY death, whether due to side effects of the treatment or due to progressive disease or due to other causes is considered as a serious adverse event.

Unexpected SAE

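### The SAE alarm in section 17.4 names a binomial test on counts for a question about incidence; read as a 50:50 test it is conservative, by an amount that depends on an SAE rate the protocol does not give

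*Protocol*

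**What the plan says.** Protocol section 17.4 opens its safety paragraph with: "The study will be closely and sequentially monitored before the interim analysis". The data are reported SAEs. Two counts are compared between arms, the patients with at least one SAE and the deaths, and the numbers of "patients with an SAE in both arms and the difference in the number of deaths in both arms are tested using the binomial test". The hypothesis is one-directional: the test asks "whether those incidences in the experimental arm are higher at a significance level of 0.05, adjusted for multiple testing (adjustment based on simulation"). The consequence is a report, not a stop: "If one of both incidences is significantly higher in the experimental arm an early report will be presented to the DSMB".

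The window runs up to the efficacy interim, which needs 12-month molecular data on the "first 150 patients (75 per treatment arm) are available, and is expected to take place 3.5-4 years after the start of the trial".

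The protocol gives no expected SAE or death rate, does not say whether the number of patients at risk enters the test, and does not give the null under which the simulation is run.

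Three other places bear on how common SAEs may be. Section 13 counts "hospitalization or prolongation of hospitalization" as serious. Section 13.2 exempts several kinds of admission from reporting. For arm B, section 9.2 says "it is advocated to admit patients clinically in case of grade 4 hematological toxicity".

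**The concern.** The hypothesis and the named test do not match. Incidence is a proportion: patients with an SAE over patients at risk. A binomial test applied to two counts ordinarily takes the total T of affected patients as given and treats arm B's share as Binomial(T, 1/2). That is the right null for rare events, where almost everyone remains event-free. Here each patient counts at most once, and the number randomised to each arm is known. When a sizeable share of patients have an SAE, the arm B count varies less under equal incidence than a coin-flip does, so the test demands more evidence than its nominal level implies.

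What is at stake is the timing of a confidential report. If the alarm is stricter than the stated 0.05, a moderate excess of patients with SAEs in the cytarabine arm could go without an early DSMB report until the interim at 3.5-4 years, although the protocol says the alarm operates at 0.05.

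**Working it through.** **Inputs from the Protocol.** One-sided 0.05, repeated testing and the binomial test (17.4); 75 per arm at the interim (17.4); balanced allocation by minimization (16); accrual of 60-70 patients per year (17.1). The only figure stated for the alarm is the 0.05 level, so that is the benchmark.

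**Assumed.** SAE incidence, varied from 10% to 70%, because the protocol gives none.

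**Step 1: variance.** With n per arm, common incidence p and T affected patients in total, the arm B count has
- coin-flip null: variance T/4;
- equal-incidence null (hypergeometric): variance (T/4) × (2n − T)/(2n − 1), which is about (T/4)(1 − p), since T is about 2np.

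The coin-flip variance is therefore too large by about 1/(1 − p). In large samples a nominal one-sided 0.05 test then has true level 1 − Φ(1.645/√(1 − p)):
- p = 0.1: 1.645/√0.9 = 1.734, level 4.1%
- p = 0.3: 1.645/√0.7 = 1.966, level 2.5%
- p = 0.5: 1.645/√0.5 = 2.326, level 1.0%
- p = 0.7: 1.645/√0.3 = 3.003, level 0.13%

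**Step 2: one worked table.** Take 30/75 patients with an SAE in arm A and 45/75 in arm B, so T = 75. The coin-flip SD is √(75/4) = 4.33. The hypergeometric SD is √(18.75 × 75/149) = 3.07. The one-sided P-value is 0.053 for the coin-flip test (no alarm) and 0.011 for Fisher's exact test.

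**Step 3: exact enumeration**, 75 per arm, one look, one-sided 0.05, summing over all pairs of binomial counts.

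False-alarm rate with equal incidence:

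| p | 50:50 binomial | Fisher | Pooled two-proportion z |
|---|---|---|---|
| 10% | 2.4% | 3.1% | 5.2% |
| 30% | 1.7% | 3.4% | 5.1% |
| 50% | 0.65% | 3.2% | 4.6% |
| 70% | 0.08% | 3.4% | 5.1% |

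Power:

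| Arm A vs arm B | 50:50 binomial | Fisher | Pooled two-proportion z |
|---|---|---|---|
| 10 vs 25% | 68% | 73% | 80% |
| 10 vs 30% | 87% | 91% | 94% |
| 20 vs 40% | 72% | 81% | 86% |
| 30 vs 50% | 59% | 77% | 82% |
| 50 vs 70% | 39% | 77% | 82% |
| 20 vs 50% | 96% | 98% | 99% |
| 30 vs 60% | 91% | 97% | 98% |
| 50 vs 80% | 82% | 98% | 99% |

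For a rare event such as 2 vs 10%, which may be closer to deaths, power is 52% for the binomial and 56% for Fisher.

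**Step 4: repeated testing.** Simulation of 4,000 trials, 65 patients per year for 3.75 years, with SAE onset assumed within 6 months of entry and a test at each new affected patient. The result depends on the null used to set the boundary.

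| Arm A vs arm B | 50:50 test, boundary set on coin-flips | 50:50 test, boundary set under equal incidence | Two-proportion test, boundary set under equal incidence |
|---|---|---|---|
| 10 vs 25% | 81% | 87% | 87% |
| 30 vs 50% | 67% | 82% | 85% |
| 50 vs 70% | 33% | 71% | 82% |

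With the coin-flip boundary the overall false-alarm rate is 3.3%, 2.0% and 0.8% at common incidences of 10%, 30% and 50%. Under equal-incidence calibration at the true rate it is 5% by construction. The test itself then costs 0, 3 and 11 points of power.

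**The case against.** The strongest reply is that the 50:50 test is an inference. Section 17.4 never conditions on the pooled count, and the next sentence speaks of incidences, so a comparison of two binomial proportions may be what was meant. That stands as a possibility. But the sentence names counts without denominators, and the two readings differ by nearly 40 points of power at 50 vs 70%, so the wording needs settling either way.

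Second, the simulation-based adjustment may already restore the level. If it draws patients under equal incidence, most of the loss goes up to about 30% incidence, and part remains at 50%. The text describes the simulation only as a correction for multiple testing, so this can be neither assumed nor ruled out.

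Third, a reader might infer that SAEs must be common because every admission counts. The documents do not support that. Section 13.2 exempts admissions for giving protocol therapy, for transfusion, for investigations and for planned procedures, while complications remain reportable. The admission advice in section 9.2 concerns arm B only and says nothing about the rate on imatinib alone. With a low control rate the loss is small: 87% versus 91% at 10 vs 30%.

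Fourth, a reader might infer that the rule misses real harm, or that it is the only safeguard before the interim. Neither holds. Excesses of about 30 points are mostly flagged. Deaths are a second trigger, section 17.3 allows unplanned analyses for the DSMB with SAE incidence by arm, and section 13.3 sends every SAE report to the study coordinator within 24 hours.

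**Conclusion.** The point holds in a conditional form. Section 17.4 names a test on counts for a hypothesis about incidences. On its ordinary 50:50 reading the alarm is conservative: modestly at about 10% incidence, materially at about 30%, and severely at 50% or more. The loss matters mainly for excesses of about 20 points on a background of 30% or higher. Power is roughly halved only near 50 vs 70%, and that should not be read as the general size of the effect.

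The conclusion rests on the 50:50 reading, on assumed SAE rates, on balanced arms and, for the sequential figures, on an assumed SAE timing. It shrinks to between 0 and 11 points of power in the scenarios examined if the boundary is calibrated under equal incidence at the true rate. It has little bearing on deaths if they are rare. This is a cheap improvement to an early-warning rule, not a fault in the trial's main design.

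**What to change.** In section 17.4, replace the binomial test for patients with an SAE by a one-sided comparison of proportions that uses the number of patients at risk in each arm: a two-proportion test, or Fisher's exact test if some remaining conservatism is acceptable (its level is 3.1-3.4% in the first table). State that the sequential boundary is calibrated by simulating patients under equal incidence, and give the range covered, for example 10-60%. The binomial test may stay for deaths. If a two-proportion test was meant all along, correcting the wording and stating the simulation null is enough.

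The cost is a sentence or two in the protocol and a rerun of the simulation. No new data are needed, because the numbers randomised are known. The downside is that the alarm will fire nearer its stated 5% when there is no true difference, so a few more confidential early reports will reach the DSMB.
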